Overview: We will conduct a 16-week RCT in primary care to preliminarily test the G-BMT intervention (8 weekly group visits) for efficacy, acceptability, and feasibility in comparison to treatment as usual (TAU) among BMT patients with persistent opioid abuse. Eighty participants with ongoing opioid abuse in office-based BMT will receive treatment intensification in the G-BMT intervention or receive TAU. We will test **efficacy** by collecting interview, urine, and medical record data examining *abstinence* (primary outcome), *retention in treatment*, and *HIV-risk behaviors*, including drug-related and sexually-related risk factors. We will test **acceptability** by assessing patient and provider satisfaction following the trial. We will test **feasibility** by examining process measures, such as *medication and visit adherence* and fidelity to the intervention manual.

Setting: The G-BMT intervention will be implemented at a single Montefiore community health center (CHC) that

offers primary and specialty care to over 15,000 adult patients. The CHC is representative of those serving low-income urban neighborhoods; over 65% of patients have public insurance and most live in the surrounding neighborhoods of the South Bronx, which are 57% Hispanic and 39% Non-Hispanic Black, and remain devastated by drug use and HIV/AIDS.⁹¹ The CHC has provided BMT to more than 700 patients since 2006, and has been used extensively for BMT-related clinical research.

Study Participants: Eligibility Criteria: 1) Currently receiving BMT at the CHC; 2) Received BMT for ≥ 12 weeks; 3) Persistent opioid abuse (urine drug testing positive for an unprescribed opioid in the previous 6 months or self-reported drug use in the previous 6 months); 4) ≥ 18 years old; 5) fluent in English or Spanish. Exclusions: 1) Contraindications to BMT (alcohol use disorder; benzodiazepine use disorder; unstable mental health condition); 2) Pregnancy; 3) Unwillingness to participate in group-based BMT.

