Treatment as usual: Participants randomized to TAU will continue to receive BMT from their PCPs based on a standardized BMT intensification protocol. Prior to the study, PCPs at the CHC will receive one hour of training on BMT intensification. The protocol will require that all BMT patients with persistent opioid abuse receive at least monthly visits with urine drug tests collected at each visit. For participants randomized to TAU, PCPs will receive an automated e-mail reminder about the following protocol. After one urine drug test is positive for opioids, PCPs will increase the frequency of visits to twice monthly with referral for behavioral counseling. After two consecutive positive tests, PCPs will increase visit frequency to weekly. After three consecutive positive tests, PCPs will refer to an addiction specialist or opioid treatment program. We will measure frequency of BMT visits, referral for behavioral counseling and referral to opioid treatment programs during the study. We will determine *observed intensity* of BMT (defined below) for exploratory analyses of treatment outcomes.

Participant tracking: To facilitate tracking participants over the 16 week follow-up period we will use tracking procedures that we developed to retain drug users in our previous research studies, in which we have had an 85% retention rate over 6-month follow-up. On Locator Forms, we will record information about: 1) participants' address and phone number; 2) contact information of participants' family members, friends, case managers, physician, pharmacy, and drug treatment program; and 3) locations where participants hang out.

Data sources and measures: A complete list of measures is listed in Table 1.

Urine Drug Testing: Research visits will include urine drug test collection, which will be used for the primary outcome (both G-BMT and TAU participants will have an equal number of research visits and urines). Urine drug tests collected during G-BMT and TAU medical visits (*clinical drug tests*) will be used for secondary outcomes.

Testing will include opiates, oxycodone, buprenorphine, methadone, cocaine, and benzodiazepines.

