Provider Satisfaction: We will adapt a previously published questionnaire to assess acceptability of the intervention to participants' PCPs. Satisfaction will be measured in three areas: overall satisfaction with BMT, perceived effectiveness of BMT intensification and support for BMT at the CHC.¹⁰¹ We will add items for PCPs with patients randomized to the G-BMT intervention to assess satisfaction with communications with the G- BMT team and likelihood of referring patients to group-based BMT in the future.

Table 1. Timing and delivery of intervention and study measures

Measure	Study Instrument	Domain	Assessment Period (week)
Urine			
Opioid use	Observed urine	-	All [†]
Questionnaires			
Sociodemographic information	BHIVES Study ⁸²	-	0
HIV Risk Behaviors	AIDS risk inventory ⁹³	-	0, 8, 16
Self-reported drug use	Addiction Severity Index ⁹⁴	-	All
Depression	CES-D ⁹⁵	-	0, 8, 16
Self-efficacy	DTCQ-8 ⁹⁶	Self-efficacy	0, 8, 12, 16
Social Support	MSPSS ⁹⁷	Outcome Expectation	0, 8, 12, 16
Buprenorphine Knowledge	10 item questionnaire	Knowledge	0, 8, 16
Quality of Life	SF-12 ⁹⁸	-	0, 8, 16
Group cohesion*	GCQ-S ⁹⁹	-	2, 4, 8
Medical Records			
Medical Visits	-	-	1-16
Buprenorphine prescriptions	-	-	1-16
Referrals	-	-	1-16
Opioid use	Clinical urine		1-8
Retention in care	-	-	0, 12, 24
Intervention Materials			
Chronic Health Conditions	-	-	0
Self-assessment forms	Check-list	Goals	1-8
Intervention fidelity	Check-list	-	1-8
Post-intervention Questionnaires			
Patient satisfaction	PCBSS ¹⁰⁰	Barriers and Facilitators	8
Provider satisfaction	5 item questionnaire ¹⁰¹	-	8
Qualitative Interviews*	Interview Guide		8

*only collected for intervention arm; [†]Study visits (2,4,6,8,12,16 weeks) CES-D = Center for Epidemiologic Studies Depression Scale; DTCQ-8 = Drug-Taking Confidence Questionnaire, 8 item version; MSPSS = Multidimensional Scale of Perceived Social Support; SF-12 = SF-12 Health Survey; GCQ-S = Group Climate Questionnaire – Short Form; PCBSS = Primary Care Buprenorphine Satisfaction Scale

Analysis:

Main outcome variables:

Primary outcome (efficacy): we will use a dichotomous measure (yes/no) of *opioid abstinence* based on 30-day self-reported opioid use following completion of the intervention and the results of urine drug tests (opiates, methadone, oxycodone) at the 8 and 12 week research visits (see Figure 1). Missing urine drug tests will be considered to be positive for opioids.

Secondary outcomes (efficacy):

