Power Analysis: Based on our experience with the preliminary model of group medical visits, we are confident that we can run five 8-week groups with an average of eight participants during the study period. Therefore, with 40 participants each in the control and interventions arm, the minimally detectable abstinence rate in the intervention arm will be 37%, based on an abstinence rate of 10% in the control arm, an intra-class correlation (ICC) of 0.01, and 80% power. This study may be underpowered to detect a significant difference in our primary outcome (abstinence), but the more important goal of this study is to estimate an effect size for the G-BMT intervention that could be used to design a larger multisite efficacy trial. Based on time and financial constraints, and our also important goals of determining feasibility and acceptability of the G-BMT intervention, we believe that recruiting a larger sample would detract from our ability to study process measures or tailor the intervention further.

Additional adaptations to the G-BMT intervention: We will use data collected in the RCT to further adapt the G-BMT intervention manual. After conducting preliminary analyses of BMT intensity and treatment outcomes, we will have a better understanding of the ideal number of visits for the G-BMT intervention. Patient satisfaction questionnaires will be used to identify specific components of the G-BMT intervention that were not as highly valued as others, and provider satisfaction questionnaires will be used to adapt the protocol for communication between the G-BMT clinicians and PCPs. Checklists evaluating fidelity of the G-BMT intervention will be used to identify components of the intervention that were not completed regularly, which may suggest lack of feasibility. We will review audio recordings of the group visits with the G-BMT clinicians and clarify the reasons for not completing these components. We will assess whether worksheets were completed between visits.

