Interview data will be collected via audio computer-assisted self-interview (ACASI) technology at baseline and during research visits 2, 4, 6, 8, 12, and 16 weeks following enrollment. *Urine samples* will be collected for drug testing at baseline and during research visits 2, 4, 6, 8, 12, and 16 weeks following enrollment. Urine drug tests will be conducted at the community health center using commercially available rapid urine drug test. At these research visits, the RA will ask subjects to provide a urine specimen in a private bathroom while the RA stands outside the door listening for tampering. Results of urine drug tests will be recorded on a standardized paper form only using the participants study ID and not other personal identifiers. *Feasibility* measures will be collected by the research assistant (RA) who will observe, time, and collect written intervention materials (e.g. self-assessment forms) from group visits. We plan to run 5 cycles of group visits, therefore, these field notes will be marked with the cycle number and group visit number but will not contain participant identifiers. *Written intervention materials* will be marked only with a study ID and transported directly to the research offices following weekly meetings between [name] (PI) and the research team. Materials will be stored in locked file cabinets. *Audio recordings* of each group visit and qualitative interviews will be collected by the RA using a digital audio-recording device. After each group visit or qualitative interview, audio recordings will be transferred to a single password protected encrypted computer and then erased from the recording device. Audio recordings will be uploaded to a secure internet portal for professional transcription and then will be transcribed with blinding of any references to personal identifiers.

Medical record data will be electronically extracting from Montefiore's centralized clinical database, and will include buprenorphine prescription data, and data on clinical visits (medical and counseling) and chronic health conditions. The electronic file will be created by Montefiore health technology staff, emailed to the PI in a password protected file, and saved on an encrypted password protected computer.

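### The urine part of the primary outcome has no test for fentanyl or other opioids outside the listed analytes, so undisclosed use of these alone is scored as abstinence

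*Combined protocol and SAP*

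**What the plan says.** Under Analysis, Main outcome variables, and again under Outcome Measures in the Data and Safety Monitoring Plan, the primary efficacy outcome is a yes/no measure of opioid abstinence. It has two components. One is self-report: the measure is "based on 30-day self-reported opioid use following completion of the intervention". The other is "the results of urine drug tests (opiates, methadone, oxycodone) at the 8 and 12 week research visits". The rule for combining the two is not stated. On missing specimens the plan says: "Missing urine drug tests will be considered to be positive for opioids".

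The full panel is given under Urine Drug Testing: "Testing will include opiates, oxycodone, buprenorphine, methadone, cocaine, and benzodiazepines". The assay is described under Data acquisition and transmission: "Urine drug tests will be conducted at the community health center using commercially available rapid urine drug test". No section names fentanyl or describes laboratory confirmation.

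The entry criterion in Section III is broader than the panel: "urine drug testing positive for an unprescribed opioid in the previous 6 months or self-reported drug use in the previous 6 months".

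**The concern.** The outcome is named for opioids in general, and entry is framed around any unprescribed opioid, but the urine evidence for the outcome is a closed list of three entries. The plan lists oxycodone and methadone beside opiates, so it does not itself treat the opiates entry as covering every opioid.

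For someone who uses only an opioid outside the list, the objective test adds nothing and the classification depends on what that person reports. The missing-equals-positive rule does not help, because the specimen was given and read as negative.

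The error runs one way: some non-abstinent participants are counted as abstinent. If this happens equally in both arms, it raises both abstinence rates and pulls the risk difference and odds ratio toward no effect. The Power Analysis section says that the more important aim is to estimate an effect size for designing a larger trial, so a biased estimate would carry into that design. If disclosure differs by arm, the bias could go either way.

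**Working it through.** **Inputs from the Power Analysis section.** Control abstinence 10%; detectable intervention abstinence 37%; 40 per arm ("with 40 participants each in the control and interventions arm"); average group size 8; ICC 0.01; power 80%. Alpha is not stated; 0.05 two-sided is assumed.

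**The plan's own figure.** Design effect = 1 + (8 − 1) × 0.01 = 1.07, so the effective n is 40 / 1.07 = 37.4 per arm. With this applied to both arms, a pooled-variance test of two proportions without continuity correction has 80% power at an intervention rate of 37.1%, and 79.9% power at 37%. The stated 37% reproduces and is not in dispute.

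**Misclassification model (assumptions, no figure in the documents).** Let s be the share of truly non-abstinent participants who use only unlisted opioids and are urine-negative at both weeks 8 and 12. Let r be the share of these who disclose use and are then scored non-abstinent. Assume also that none of the listed strips reacts to these opioids; the documents give no cross-reactivity. The share wrongly scored abstinent is

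f = s × (1 − r)

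and, for a true rate p,

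measured rate = p + (1 − p) × f.

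Three combinations span the range:
- s = 10%, r = 80%: f = 0.10 × 0.20 = 0.02
- s = 20%, r = 50%: f = 0.20 × 0.50 = 0.10
- s = 30%, r = 50%: f = 0.30 × 0.50 = 0.15

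Worked case, f = 0.10: control 0.10 + 0.90 × 0.10 = 0.190; intervention 0.37 + 0.63 × 0.10 = 0.433; odds ratio (0.433 / 0.567) / (0.190 / 0.810) = 3.3.

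| f (equal in both arms) | TAU | G-BMT | Difference, points | Odds ratio | Power, design effect on both arms |
|---|---|---|---|---|---|
| 0 | 10.0% | 37.0% | 27.0 | 5.3 | 79.9% |
| 0.02 | 11.8% | 38.3% | 26.5 | 4.6 | 76.3% |
| 0.05 | 14.5% | 40.2% | 25.7 | 4.0 | 70.9% |
| 0.10 | 19.0% | 43.3% | 24.3 | 3.3 | 62.5% |
| 0.15 | 23.5% | 46.5% | 23.0 | 2.8 | 54.9% |

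With equal f the difference shrinks by the factor (1 − f). The odds ratio falls proportionally more, because the low control rate moves most.

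**If f differs by arm.** Measured difference = 27 + 63 × f(G-BMT) − 90 × f(TAU), in points. With f = 0.05 in TAU only it is 27 − 4.5 = 22.5. With f = 0.05 in G-BMT only it is 27 + 3.15 = 30.15. The documents give no basis for choosing a direction.

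**The case against.** The strongest reply is that the premise comes from outside the plan. Fentanyl is not mentioned; the background names opioid analgesics and heroin. No prevalence of use outside the panel is given. This stands as far as size is concerned: s and r are assumptions. It does not remove the gap, which can be read directly from the analyte list.

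Second, urine is only part of the outcome. Self-report is not limited to three analytes, and it is taken by computer-assisted self-interview. A reader might infer that the endpoint measures abstinence from three drug classes rather than opioid abstinence. The documents do not support that: a user who discloses can be scored non-abstinent, although the unstated combining rule leaves even this open. The exposure is confined to participants who use only unlisted opioids, test negative at both visits and do not disclose.

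Third, selection narrows the group at risk. Participants enter through a positive urine test or self-reported drug use, so someone who conceals use and takes only unlisted opioids would not readily qualify. Switching after entry remains possible, but this argues against assuming a large s.

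Fourth, the effect may be small beside sampling error. Ignoring clustering, the standard error of a 10% vs 37% difference is √[(0.10 × 0.90 + 0.37 × 0.63) / 40] = 9.0 points, against a bias of 0.5 to 4 points in the table. That is fair for a pilot, and the plan says it may be underpowered. But the bias does not shrink with sample size, and it enters the estimate carried into the next trial.

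Two further inferences go beyond the text. One is that synthetic opioids as a class are untested; methadone is synthetic and is on the panel. The other is that the clinical escalation steps in both arms would miss the same use. The steps after one and two positives are written for the TAU arm only, and it is not certain that urine tests at clinical visits use the research panel.

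**Conclusion.** The point holds in limited form. The urine component of the primary outcome cannot detect fentanyl or other opioids outside the listed analytes, and for a participant using only these, self-report is the sole check. Undisclosed use of this kind is counted as abstinence.

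Under equal misclassification of 2% to 15% of non-abstinent participants, the 27-point difference is measured as 26.5 to 23.0 points and the odds ratio of 5.3 as 4.6 to 2.8. These figures rest on assumed s and r, on equal f in both arms, on disclosed use being scored non-abstinent, and on the listed strips not reacting to the unlisted opioids. They show what could happen; they do not estimate what will. At the lower end the effect is minor. The case for acting is that the remedy is cheap and uses specimens already in hand.

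**What to change.** - Add a fentanyl strip to the rapid test on urine already collected at the week 8 and week 12 research visits. Week 0 is optional and for description only. Count an unprescribed positive as opioid-positive, and state how a prescription is established.
- Report the three-analyte outcome, as now defined, for all participants in both arms, so that definitions do not mix across group cycles. Report the fentanyl-inclusive outcome alongside it for those tested. Make it primary only if the strip is in place for every participant; otherwise prespecify it as a sensitivity analysis.
- State that a specimen given before the strip was introduced is untested for fentanyl, not missing, so that the missing-equals-positive rule does not apply to it.
- If no strip is added, say wherever the result is reported that urine verified only opiates, methadone and oxycodone, and that other opioid use rests on self-report alone. Renaming the outcome as abstinence from three drug classes would misdescribe it, because the self-report is broader.

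Cost: 80 × 2 = 160 strips at most, or 80 × 3 = 240 with week 0; a short amendment; and a slightly lower measured abstinence rate. No new visit or specimen is needed. The change concerns research-visit measurement only and leaves every clinical rule as written.

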We have developed a preliminary model of BMT group medical visits, conducted focus groups with BMT patients and providers, and we will use this data to develop a manualized group-based BMT intervention (G-BMT). We will then conduct an RCT of the G-BMT intervention within primary care to preliminarily test its efficacy, acceptability, and feasibility. Participants who have persistent opioid abuse while receiving BMT in primary care will be randomized to the G-BMT intervention (40 participants in 5 groups) or to intensify BMT (treatment as usual) with their individual primary care physician (40 participants). The specific aims for this developmental study include:

Aim 1: To develop the G-BMT intervention for primary care

[name] G-BMT 2-6-18

We will adapt a preliminary model of BMT group medical visits to meet the needs of opioid users with persistent opioid abuse.

Aim 2: To pilot test G-BMT for efficacy, acceptability, and feasibility in an RCT within primary care H1: In a 16-week RCT of G-BMT, participants who receive the G-BMT intervention (vs. treatment as usual) will have higher abstinence rates (primary outcome, efficacy), fewer HIV risk behaviors (efficacy), and greater satisfaction with treatment (acceptability) and adherence to medical visits (feasibility).

II. Background and Significance

In 2010, drug overdose replaced motor vehicle accidents as the leading cause of accidental death in the United States.³⁴ This epidemic has primarily been driven by opioid addiction, with opioid analgesic use, misuse, and overdose tripling between 1999 and 2010.¹ Opioid analgesic overdose deaths reached nearly 17,000 in 2010, the latest year that data is available, while heroin overdoses likely cause an additional 2,000 deaths annually.^{3,35} As regulations regarding opioid analgesic prescribing have become more restrictive, heroin use and overdose have also seen increases. In New York City, between 2011 and 2012, opioid analgesic overdose deaths decreased by 12%, while between 2010 and 2012, heroin overdose deaths increased by 71% and remain the leading cause of drug overdose death.³⁶ In the United States, opioid addiction is a public health crisis with its epicenter in New York City.

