Questionnaire: ACASI technology, which plays an audio recording of questions as it displays the question on a computer screen, will be used by the RA to administer questionnaires. After completing the trial, participants and providers will be assessed for satisfaction with treatment. Interviews will take 30-60 minutes depending on the study visit.

Qualitative Interview: We will conduct 20 in-depth semi-structured interviews with persons who have completed the G-BMT intervention in order to better understand the impact of the group buprenorphine maintenance treatment. Interviews will be audio recorded. Interviews will take 45-60 minutes to complete.

Medical records: We will extract electronic medical record data, including visit and prescription information, from Montefiore's health center to assess *medication and visit adherence, treatment retention* (see below) and to determine the *observed intensity* of BMT, defined as the number of medical or counseling visits attended during the study period for the TAU arm and the number of group visits attended for the G-BMT arm.

Intervention Materials: The RA will also attend group visits to assess fidelity using a checklist derived from the intervention manual. The RA will document completion of each G-BMT component, time spent on components, and use the checklist to rate facilitators on fidelity to the intervention. The RA will also record participants' attendance, completion of self-assessment forms, and engagement in intervention activities (e.g. # of times gave personal updates). Group cohesion will be measured as part of the ACASI interviews. All group visits will be audio-recorded and at least 25% of recordings will be reviewed by the PI to confirm the assessment of intervention fidelity.

Post-intervention Questionnaires:

Patient Satisfaction: We will adapt a previously published questionnaire that assesses satisfaction with BMT in primary care.¹⁰⁰ Satisfaction is measured in three areas: overall satisfaction, staff expertise/ responsiveness, and helpfulness of treatment. We will adapt the helpfulness domain to address specific components of the G-BMT intervention (e.g. self-assessment forms), and add items that assess privacy and confidentiality.

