- a.) *Retention in treatment* will be used to determine whether participants remain in BMT following the specified time intervals. *Three month retention* will be defined as having a medical visit or active

buprenorphine prescription 12-16 weeks after study initiation (one month after G-BMT intervention completion). *Six month retention* will be assessed at 24-28 weeks after study initiation.

b.) *Changes in HIV risk behaviors* will be based on the AIDS risk inventory, which includes questions regarding frequency of injection drug use, number of times sharing syringes, number of sexual partners, and frequency of unprotected sex. We will assess risk behaviors at completion of the G-BMT intervention (8 week visit) and two months following completion of the intervention (16 week visit).

Primary outcome (acceptability): Overall satisfaction with BMT will be measured on a 5-point Likert scale for participants and providers.

Primary outcome (feasibility): We will compare *medication and visit adherence* between the G-BMT and TAU arms as the primary measure of feasibility. Medication adherence will be determined from medical record data based on lapses in BMT defined as the number of days without an active buprenorphine prescription during the study. Visit adherence will be defined as the proportion of obligated medical visits (as per G-BMT or TAU protocol) attended. Other important measures of feasibility are listed in Table 2 and will be used as secondary outcomes and to assess fidelity to the G-BMT intervention.

G-BMT component	Measure	Assessment
Overall	Participant engagement # urine drug tests collected Time per group medical visit	RA conducted EMR Timed
Buprenorphine Education	Fidelity to intervention Time for education	Checklist Timed
Self-management skills	Self-assessment forms Fidelity to intervention Time for instruction	Collected Checklist Timed
Peer Support	Personal Updates Feedback to other participants Group Cohesion Time for facilitated discussion	RA observed RA observed GCQ-S* Timed
Medication Management	# non-BMT medical complaints # individual physical exams Time for medical management	EMR RA observed Timed
*assessed as part of ACASI interviews		

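### Patient satisfaction, the primary acceptability outcome, is measured only at week 8 with no baseline, which costs precision; the text also places it after the 16-week trial, which conflicts with Table 1

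*Combined protocol and SAP*

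**What the plan says.** **Status and hypothesis.** Section III (Analysis) and section IV (Outcome Measures) both give the primary acceptability outcome as "Overall satisfaction with BMT will be measured on a 5-point Likert scale for participants and providers". H1 under Aim 2 makes it a between-arm claim: G-BMT participants are expected to show "greater satisfaction with treatment (acceptability) and adherence to medical visits (feasibility").

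**Schedule.** The Table 1 row reads "Patient satisfaction PCBSS ¹⁰⁰ Barriers and Facilitators 8", that is, week 8 and no week 0. Depression, self-efficacy, social support, buprenorphine knowledge, quality of life and HIV risk behaviors all have a week 0 assessment in the same table.

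**Experience at entry.** The eligibility criteria require current BMT at the health center and, as a separate item, "Received BMT for ≥ 12 weeks".

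**Timing in the text.** The Questionnaire paragraph says "After completing the trial, participants and providers will be assessed for satisfaction with treatment". The section III Overview speaks of "assessing patient and provider satisfaction following the trial", and the Protocol Summary in section IV repeats this. The same Overview states: "We will conduct a 16-week RCT in primary care to preliminarily test the G-BMT intervention (8 weekly group visits"). The paragraph on interaction between PCPs and the research team returns care to the PCP once the group intervention is complete.

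**The concern.** There are two separate points.

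First, overall satisfaction with BMT is something that all participants can already rate at entry. A prior rating is usually a candidate predictor of a later one. Because it is not collected, neither description of the analysis can adjust for it. Section III allows for covariates that differ between arms, and section IV names depressive symptoms and sociodemographic variables. With the sample fixed at 40 per arm for reasons of time and money, a baseline covariate is one of the few ways left to sharpen this comparison.

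Second, the protocol gives two times for one outcome. Staff working from Table 1 would collect it at the end of the group visits. Staff working from the Questionnaire paragraph could collect it at or after week 16. These are different outcomes for the G-BMT arm, because the later rating would follow a return to individual care.

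**Working it through.** **The plan's own figure.** The documents give no power or precision figure for satisfaction. The only power statement concerns abstinence: 37% detectable against 10%, with 40 per arm, ICC 0.01 and 80% power. With a design effect of 1 + (8 − 1) × 0.01 = 1.07 on both arms and a two-sided 5% test (assumed, since no alpha is stated), the detectable rate is 37.1%, so that figure reproduces. It has no bearing on satisfaction.

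**Precision: inputs.** 40 per arm (Power Analysis). Assumed: two-sided 5%, 80% power, a rating from every participant, the score treated as continuous, and a correlation *r* between baseline and week 8.

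**Formulas.**
- Residual variance removed by adjustment: *r*².
- Equivalent gain in sample size: 1/(1 − *r*²) − 1.
- Detectable difference in SD units: (1.960 + 0.842) × √(1 − *r*²) × √(1/40 + 1/40). With no baseline this is 2.802 × 0.2236 = 0.63.
- Power at a true difference of 0.5 SD: Φ(0.5 / [0.2236 × √(1 − *r*²)] − 1.960).

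| *r* (assumed) | Variance removed | Equivalent extra sample | Detectable difference (SD) | Power at 0.5 SD |
|---|---|---|---|---|
| no baseline | 0% | 0% | 0.63 | 61% |
| 0.1 | 1% | 1% | 0.62 | 61% |
| 0.3 | 9% | 10% | 0.60 | 65% |
| 0.5 | 25% | 33% | 0.54 | 73% |
| 0.6 | 36% | 56% | 0.50 | 80% |

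Applying the 1.07 design effect to the G-BMT arm only (40/1.07 = 37.4 effective participants) changes little: 0.64 SD with no baseline, 0.61 at *r* = 0.3 and 0.55 at *r* = 0.5.

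**If the correlation differs by arm.** Suppose *r* = 0.5 under TAU and 0.1 under G-BMT, with equal variances and arm sizes. The pooled slope is (0.5 + 0.1)/2 = 0.3.
- TAU residual variance: 1 + 0.3² − 2 × 0.3 × 0.5 = 0.79.
- G-BMT residual variance: 1 + 0.3² − 2 × 0.3 × 0.1 = 1.03.
- Average: 0.91, a 9% reduction, equivalent to about 10% more participants. This is far below the 33% that a common *r* of 0.5 would give.

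**Timing: the passages side by side.**
- Table 1 and its heading, Post-intervention Questionnaires: week 8, for patients and providers alike.
- The Questionnaire paragraph, the Overview and the Protocol Summary: after or following the trial.
- The HIV risk outcome separates the two time points. It treats the 8-week visit as completion of the intervention and the 16-week visit as two months later.
- The gap is 16 − 8 = 8 weeks. BMT care passes back to the PCP at the start of it.

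**The case against.** The strongest reply is that nothing here is invalid. Measuring an outcome only after randomization gives an unbiased comparison, and the unadjusted standard error already allows for chance imbalance. A reader might infer that the missing baseline biases the result or lets imbalance through uncorrected; the design does not support that. This part of the objection stands in full, so the point concerns precision only.

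The size is also uncertain. At week 0 everyone would rate existing individual care, whereas at week 8 the G-BMT arm rates a new format with different clinicians. The baseline may therefore predict poorly in that arm, as the unequal-correlation case shows. This stands, and it is why the range starts at 1%.

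Two further inferences go beyond the text. The criteria do not say that the 12 weeks of BMT were at this center, so some participants may have had less experience of its care. Nor is overall satisfaction stated to be a single item: it is one of three areas of a published questionnaire, scored on a 5-point scale.

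Satisfaction is also primary only within the acceptability domain. Abstinence is the trial's main efficacy outcome, and the plan puts estimation ahead of testing. Items about specific G-BMT components cannot be asked before exposure. That is true, but the overall question can be.

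On timing, the only explicit schedule is Table 1. The questionnaire heading agrees with it, and no research visit is planned beyond week 16. The other sentences are summaries in which trial probably means intervention. A reader might infer that the G-BMT rating will in fact reflect PCP care, but that would require staff to set the schedule table aside. The same list that returns care to the PCP also says that participants do not see the PCP for BMT during the study period, so even the literal reading is not free of ambiguity. What remains is a conflict in wording that should be removed.

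**Conclusion.** The point holds as a modest, inexpensive improvement. An outcome labelled primary for acceptability and compared between arms has no baseline, although participants could rate overall satisfaction at enrollment. The cost is precision: about 1% to 36% of residual variance for an assumed correlation of 0.1 to 0.6. In detectable-difference terms, 0.63 SD could fall to between 0.62 and 0.50 SD. These figures rest on assumed correlations, a two-sided 5% level and complete data from 40 per arm; the documents supply only the arm size. The true gain could be near the bottom of the range.

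The timing conflict is real on the page but probably loose wording. If the after-the-trial sentences were followed, the G-BMT rating would come after about 8 weeks of PCP care and could dilute the contrast that H1 tests. The documents do not show that this will happen, and they do not support a claim that the week 8 comparison is biased.

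**What to change.** 1. Add the overall-satisfaction question or questions to the week 0 ACASI interview, answered before allocation is known. Leave the G-BMT component items at week 8 only.
2. State the analysis of satisfaction: compare arms at week 8 in an ordinal or linear mixed model with baseline satisfaction as a covariate. The plan's primary-outcome model names only abstinence as the dependent variable, so this also supplies a model that is not explicitly given now. Use a missing indicator for participants enrolled before the change. Their baseline is absent because of enrollment date, not arm, so the randomized comparison is preserved.
3. Reword the section III Overview, the Questionnaire paragraph and the section IV Protocol Summary so that satisfaction is assessed at week 8, on completion of the intervention, as in Table 1.

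The cost is one or a few extra baseline questions, a short protocol amendment and three changed sentences. Participants already enrolled will have no baseline value, which reduces the gain. If enrollment is complete, only the rewording and the stated week 8 model (without the baseline covariate) remain useful.
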